#### 11.0 STUDY MANAGEMENT

#### 11.1 Conflict of Interest

Any investigator who has a conflict of interest with this study (patent ownership, royalties, or financial gain greater than the minimum allowable by their institution, etc.) must have the conflict reviewed by the UTSW COI Committee and IRB according to UTSW Policy

on Conflicts of Interest. All investigators will follow the University conflict of interest policy.

#### 11.2 Institutional Review Board (IRB) Approval and Consent

It is expected that the IRB will have the proper representation and function in accordance with federally mandated regulations. The IRB must approve the consent form and protocol.

In obtaining and documenting informed consent, the investigator should comply with the applicable regulatory requirement(s), and should adhere to Good Clinical Practice (GCP) and to ethical principles that have their origin in the Declaration of Helsinki.

Before recruitment and enrollment onto this study, the subject will be given a full explanation of the study and will be given the opportunity to review the consent form. Each consent form must include all the relevant elements currently required by the FDA Regulations and local or state regulations. Once this essential information has been provided to the subject and the investigator is assured that the subject understands the implications of participating in the study, the subject will be asked to give consent to participate in the study by signing an IRB-approved consent form.

Prior to a patient's participation in the trial, the written informed consent form should be signed and personally dated by the subject and by the person who conducted the informed consent discussion.

#### 11.3 Registration Procedures

All subjects must be registered with the Radiation Oncology Research Office before enrollment to study. Prior to registration, eligibility criteria must be confirmed with the Radiation Oncology Study Coordinator. To register a subject, call [contact] Monday through Friday, 9:00AM-5:00PM.

New subjects will receive a number beginning with 001 upon study consent such that the first subject consented is numbered 001, the second subject consented receives the number 002, etc.

Upon confirmation of eligibility and enrollment as per the afore-mentioned instructions, the subject will be assigned a secondary number in the order of enrollment. For example, subject 001 will become 001-01 upon enrollment. If subject 002 screen fails, and subject 003 is the next subject enrolled, subject 003 will become 003-02 and so-on.

Each newly consented subject should be numbered using the schema provided above. Upon registration, the registrar will assign the additional registration code according to the numbering schema outlined above, which should then be entered as the patient study id in Velos upon updating the status to enrolled.

The numbering schema should clearly identify the site number; the sequential number of the subject enrolled as well as the status of the subjects enrolled so that the number of subjects consented versus the number of subjects actually enrolled may be easily identified.

#### 11.4 Data Management and Monitoring/Auditing

REDCap is the UTSW SCCC institutional choice for the electronic data capture of case report forms for SCCC Investigator Initiated Trials. REDCap will be used for electronic case report forms in accordance with Simmons Comprehensive Cancer Center requirements, as appropriate for the project

The Medical Oncologist investigators and delegates, will perform an Immunotherapy Assurance Review of all patients in this trial. The Radiation Oncologist investigators and delegates, will perform an RT Quality Assurance Review after the first 20 cases enrolled. Subsequent reviews will continue in a periodic and timely fashion. The final cases will be reviewed within 3 months after this study has reached the target accrual. The goal of the review is to evaluate protocol compliance. The scoring mechanism is: Per Protocol, Variation Acceptable, and Deviation Unacceptable.

The UTSW Simmons Comprehensive Cancer Center (SCCC) Data Safety Monitoring Committee (DSMC) is responsible for monitoring data quality and patient safety for all UTSW SCCC clinical trials. As part of that responsibility, the DSMC reviews all local serious adverse events and UPIRSOs in real time as they are reported and reviews adverse events on a quarterly basis. The quality assurance activity for the Clinical Research Office provides for periodic auditing of clinical research documents to ensure data integrity and regulatory compliance. A copy of the DSMC plan is available upon request.

The SCCC DSMC meets quarterly and conducts annual comprehensive reviews of ongoing clinical trials, for which it serves as the DSMC of record. The QAC works as part of the DSMC to conduct regular audits based on the level of risk. Audit findings are reviewed at the next available DSMC meeting. In this way, frequency of DSMC monitoring is dependent upon the level of risk. Risk level is determined by the DSMC Chairman and a number of factors such as the phase of the study; the type of investigational agent, device or intervention being studied; and monitoring required to ensure the safety of study subjects based on the associated risks of the study. Protocol-specific DSMC plans must be consistent with these principles.

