#### 4.4.8 Compliance Criteria

The compliance criteria listed below will be used to score each case. Given the limitations inherent in the treatment planning process, the numbers given in this section can be different than the prescription table. The Per Protocol and Variation Acceptable categories are both considered to be acceptable. The Per Protocol cases can be viewed as ideal plans, and the Variation Acceptable category can include more challenging plans that do not fall at or near the ideal results. A final category, called Deviation Unacceptable, results when cases do not meet the requirements for either Per Protocol or Variation Acceptable. Plans falling in this category are considered to be suboptimal and additional treatment planning optimization is recommended.

Target Volume Constraints and Compliance Criteria

Name of Structure	Dosimetric parameter	Per Protocol	Variation Acceptable
PTV_6000	D95%(Gy)	60	58.8 to 61.2Gy (excluding 60 Gy)
	*Dmin(Gy)	≥ 57	≥54 Gy
	*Dmax(Gy)	≤ 72	≤75 Gy

\* Dmin and Dmax values are for a volume of 0.03 cc.

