**Delivery Compliance Criteria** 

Delivery Compliance Criteria		
	Per Protocol	Variation
		Acceptable
Start date (days after step 1 registration)	14 days	15-30 days
RT Elapsed Days	< 45 days	46-51 days
Interruptions (other than holidays or weekends)	0-2 days	3-7 days

**Note**: Cases will be scored as Deviation Unacceptable when the time limits given above are not met.

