#### 10.3.4 Interim Reports to Monitor the Study Progress

Interim reports with descriptive statistics will be prepared twice a year until the initial manuscript reporting the treatment results has been accepted for publication. In general, the interim reports will contain information about the patient accrual rate with a projected completion date for the accrual phase; data quality; compliance rate of treatment delivery with the distributions of important prognostic baseline variables; and the frequencies and severity of adverse events.

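### The radiotherapy elapsed-days rule scores a 45-day course worse than a 51-day one; secondarily, the first radiotherapy quality review waits for 20 of 50 enrolments

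*Combined protocol and SAP*

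**What the plan says.** **Scoring of delivery.** The Delivery Compliance Criteria table in Section 4.4.8 has three rows: start date, "RT Elapsed Days" and interruptions. For elapsed days, Per Protocol is strictly fewer than 45 and Variation Acceptable is 46 to 51. The note beneath reads "Cases will be scored as Deviation Unacceptable when the time limits given above are not met". The plan does not say whether the first treatment day counts as day 0 or day 1.

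**Timing of review.** In Section 11.4 the radiation oncologist investigators and delegates "will perform an RT Quality Assurance Review after the first 20 cases enrolled". After that, "Subsequent reviews will continue in a periodic and timely fashion", and "The final cases will be reviewed within 3 months after this study has reached the target accrual". No interval or case count is given for the reviews in between. The same paragraph has the medical oncologists run a durvalumab review without any such threshold: it "will perform an Immunotherapy Assurance Review of all patients in this trial". No earlier radiotherapy review is described elsewhere. Sections 4.4.5 and 4.4.8 require contours to be submitted with the plan and each case to be scored, but set no earlier review time.

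**Use of the score.** Section 10.3.4 says the twice-yearly interim reports will in general include the "compliance rate of treatment delivery with the distributions of important prognostic baseline variables".

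**The concern.** A compliance scale should not improve as the course gets longer. As written, it goes from Per Protocol at 44 days to Deviation Unacceptable at 45, then back to acceptable at 46. A patient could gain a better grade by missing one more day. The reported radiotherapy compliance rate would then be wrong for any patient who finished on day 45.

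The second part concerns safety more than statistics. The regimen gives a checkpoint inhibitor together with thoracic radiotherapy, and Section 1.2 names pneumonitis as arguably the chief worry when thoracic chemoradiation and checkpoint inhibition are combined in sequence. If a contouring or planning error is systematic, and the treating team shares it and so does not see it, the Section 11.4 review is the one described check that would look for it across cases. That review begins only after two fifths of the trial has enrolled.

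**Working it through.** **Inputs.** N = 50 and 3 years of accrual (Section 10.2); first review after 20 cases (Section 11.4); 30 fractions (Section 4.4.7); elapsed-days and interruption limits (Section 4.4.8). Assumptions: one fraction per weekday, and uniform accrual where a month is given.

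**Plan's own figure.** 47 / (1 − 0.05) = 49.5, rounded up to 50. The stated total reproduces.

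**Step 1. Apply the limits to each whole day.**

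| Elapsed days | Category as written |
|---|---|
| 44 or fewer | Per Protocol |
| 45 | Deviation Unacceptable (by the note) |
| 46 to 51 | Variation Acceptable |
| 52 or more | Deviation Unacceptable |

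The interruptions row, by contrast, has no hole: 0–2 days, then 3–7.

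**Step 2. Is 45 days reachable?** With m missed weekdays, the course ends on the (30 + m)th weekday from the start.

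- No missed days: 39 or 41 days as last date minus first date, or 40 or 42 with the first day counted as day 1. Never 45.
- First day as day 1: a Monday, Tuesday or Wednesday start with m = 3 gives 45. For Monday, 33 weekdays are 6 full weeks plus 3 days, so the course ends on 42 + 3 = 45.
- First day as day 0: a Monday or Tuesday start with m = 4, or a Friday start with m = 2, gives 45. For Friday, 32 weekdays are 1 + 30 + 1, so the course ends on the seventh Monday, which is day 46 counted from 1 and day 45 counted from 0.

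**Step 3. Two consequences.**

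- Order: for a Friday start counted from 0, 2 missed days give 45 (Deviation Unacceptable), while 3 give 46 (Variation Acceptable).
- Counting: a Monday start with 3 missed days is Per Protocol at 44 counted from 0, and Deviation Unacceptable at 45 counted from 1.

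On the interruptions row, 2 missed days are Per Protocol and 3 or 4 are Variation Acceptable. That row excludes holidays, so a Friday start with two holidays reaches 45 (counted from 0) with no counted interruption. In all these cases, if the start-date row is met, the elapsed-days row alone produces the worst grade.

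**Step 4. Size.** One misgraded course changes the rate by 1/50 = 2 percentage points, if all 50 patients are in the denominator. The documents give no basis for how many courses will end on day 45; none would be 0 points and three would be 6.

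**Step 5. Review timing.** 20/50 = 40%. At a uniform 50/36 = 1.39 per month, the 20th patient enrols at 20/1.39 = month 14.4. At an assumed 2 or 1 per month over that stretch it would be month 10 or month 20. The 40% does not depend on the rate. A first review after 5 cases would fall at 5/50 = 10% of enrolment, or month 5/1.39 = 3.6 under uniform accrual.

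**The case against.** The strongest reply is that the first part is a one-day boundary slip and the second a preference about audit frequency. Much of that is fair.

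- **Reach of the scoring gap.** A reader might infer that ordinary courses are misgraded. They are not: an uninterrupted course never lasts 45 days, and most routes to 45 already carry a Variation Acceptable on interruptions unless the missed days are holidays. The score also feeds no endpoint, analysis population, power calculation or stopping rule in Section 10. What stands is that the rule gives a wrong grade at a reachable value.
- **The sign.** If the source PDF prints a less-than-or-equal sign, the gap closes. The neighbouring tables in Section 4.4.8 do print that sign, so the strict one is probably genuine, but it needs checking.
- **Re-planning.** A reader might infer that the advice in Section 4.4.8 that "additional treatment planning optimization is recommended" is defeated because review comes too late. The documents do not tie that advice to the Section 11.4 review, whose stated goal is to evaluate compliance. Sections 4.4.7 and 4.4.9 already direct planners to work with the constraints during planning.
- **Interim reports.** Under uniform accrual, about 6 × 1.39 = 8 and 12 × 1.39 = 17 patients would be enrolled at months 6 and 12, with no radiotherapy case yet reviewed under Section 11.4. A reader might infer that those reports could not be completed. Section 10.3.4 only describes their contents in general terms, and start dates, elapsed days and interruptions can come from treatment records.
- **Other safeguards.** Exclusions 3.2.10 and 3.2.11 act on planned lung and heart dose, Section 11.3 requires eligibility to be confirmed before registration, Section 11.8 has the Principal Investigator oversee every patient's treatment, and the monitoring committee reviews serious events in real time and adverse events quarterly. These weaken the safety argument. They do not remove it, because none is described as an across-case check of contours and plans.

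**Conclusion.** The scoring gap holds on the text: 45 elapsed days is Deviation Unacceptable while 46 to 51 is acceptable, and 2 to 4 missed weekdays can produce it. Its effect is confined to the descriptive compliance rate, at 2 percentage points per affected patient on a denominator of 50. This rests on the strict sign being the printed one and on one fraction per weekday.

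The review timing is secondary: a cheap improvement rather than an error. Forty per cent of patients enrol before the first radiotherapy review. The month (about 14) depends on uniform accrual, which the plan does not state. The supported risk is limited to a systematic error that also passes the treating team's own checks. Neither part alters the sample size, power or significance level.

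**What to change.** **Delivery table (Section 4.4.8).** Check the sign in the elapsed-days row against the source PDF. If it is strict, the sponsor should reconcile the two limits so that every whole-day value falls in exactly one category and the grade never improves as the course lengthens. State whether the first treatment day is day 0 or day 1. Where the limit should lie is for the sponsor; none is proposed here. The cost is a small table edit and one sentence.

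**Review schedule (Section 11.4).** Have the same reviewers take the first batch earlier, for example after about 5 cases, and then review the accumulated cases before each twice-yearly report. The number of case reviews is unchanged; the cost is more, smaller sessions.

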#### 11.5 Adherence to the Protocol

Except for an emergency situation, in which proper care for the protection, safety, and well-being of the study subject requires alternative treatment, the study shall be conducted exactly as described in the approved protocol.

- **11.5.1 Exceptions** (also called single-subject exceptions or single-subject waivers): include any departure from IRB-approved research that is *not due to an emergency* and is:
  - intentional on part of the investigator; or
  - in the investigator's control; or
  - not intended as a systemic change (e.g., single-subject exceptions to eligibility [inclusion/exclusion] criteria)
- □ Reporting requirement: Exceptions are non-emergency deviations that require *prospective*IRB approval before being implemented. Call the IRB if your request is urgent.

  If IRB approval is not obtained beforehand, this constitutes a major deviation.
  - **11.5.2 Emergency Deviations:** include any departure from IRB-approved research that is necessary to:
    - avoid immediate apparent harm, or
    - protect the life or physical well-being of subjects or others
      - □ **Reporting requirement**: Emergency deviations must be promptly reported to the IRB within 5 working days of occurrence.

- **11.5.3 Major Deviations** (also called **violations**): include any departure from IRB-approved research that:
  - Harmed or placed subject(s) or others at risk of harm (i.e., did or has the
    potential to negatively affect the safety, rights, or welfare of subjects or others),
    or
  - Affect data quality (e.g., the completeness, accuracy, reliability, or validity of the data) or the science of the research (e.g., the primary outcome/endpoint of the study)
    - □ **Reporting requirement**: Major deviations must be promptly reported to the IRB within 5 working days of PI awareness.

#### **11.5.4 Minor Deviations:** include any departure from IRB-approved research that:

- Did not harm or place subject(s) or others at risk of harm (i.e., did not or did not have the potential to negatively affect the safety, rights, or welfare of subjects or others), or
- Did not affect data quality (e.g., the completeness, accuracy, reliability, or validity of the data) or the science of the research (e.g., the primary outcome/endpoint of the study)
  - □ **Reporting requirement**: Minor deviations should be tracked and summarized in the progress report at the next IRB continuing review.

#### 11.6 Amendments to the Protocol

Should amendments to the protocol be required, the amendments will be originated and documented by the Principal Investigator. A summary of changes document outlining proposed changes as well as rationale for changes, when appropriate, is highly recommended. When an amendment to the protocol substantially alters the study design or the potential risk to the patient, a revised consent form might be required.

The written amendment, and if required the amended consent form, must be sent to the IRB for approval prior to implementation.

#### 11.7 Record Retention

Study documentation includes all Case Report Forms, data correction forms or queries, source documents, Sponsor-Investigator correspondence, monitoring logs/letters, and regulatory documents (e.g., protocol and amendments, IRB correspondence and approval, signed patient consent forms).

Source documents include all recordings of observations or notations of clinical activities and all reports and records necessary for the evaluation and reconstruction of the clinical research study.

Government agency regulations and directives require that the study investigator retain all study documentation pertaining to the conduct of a clinical trial. In the case of a study with a drug seeking regulatory approval and marketing, these documents shall be retained for at least two years after the last approval of marketing application in an International Conference on Harmonization (ICH) region. In all other cases, study documents should be kept on file until three years after the completion and final study report of this investigational study.

#### 11.8 Obligations of Investigators

The Principal Investigator is responsible for the conduct of the clinical trial at the site in accordance with Title 21 of the Code of Federal Regulations and/or the Declaration of Helsinki. The Principal Investigator is responsible for personally overseeing the treatment

of all study patients. The Principal Investigator must assure that all study site personnel, including sub-investigators and other study staff members, adhere to the study protocol and all FDA/GCP/NCI regulations and guidelines regarding clinical trials both during and after study completion.

The Principal Investigator at each institution or site will be responsible for assuring that all the required data will be collected and entered onto the Case Report Forms. Periodically, monitoring visits may be conducted and the Principal Investigator will provide access to his/her original records to permit verification of proper entry of data. At the completion of the study, all case report forms will be reviewed by the Principal Investigator and will require his/her final signature to verify the accuracy of the data.

#### 13.0 APPENDICES

APPENDIX I. Dosing Modification and Toxicity Management Guidelines for Immune-Mediated, Infusion-Related, and Non-immune-mediated reaction.

Toxicity Management Guidelines (TMGs)

Drug Substance Durvalumab and Tremelimumab

TMG Version 21 September 2023

## **ANNEX TO PROTOCOL**

Dosing Modification and Toxicity Management Guidelines (TMGs) for Durvalumab Monotherapy, Durvalumab in Combination with other Products, or Tremelimumab Monotherapy

Note: Annex is to be used in any clinical trial protocol within which patients are treated with Durvalumab Monotherapy, Durvalumab in Combination with other Products, or Tremelimumab Monotherapy

#### **Version History**

## September 2023

The Toxicity Management Guidelines (TMGs) have been developed to assist investigators with the recognition and management of toxicities associated with use of the immune-checkpoint inhibitors durvalumab [MEDI4736] (PD-L1 inhibitor) and tremelimumab (CTLA-4 inhibitor). Given the similar underlying mechanism of toxicities observed with these two compounds, these TMGs are applicable to the management of patients receiving either drug as monotherapy or both drugs in combination. Additionally, these guidelines are applicable when either durvalumab or tremelimumab or a combination of these two immune checkpoint inhibitors (ICI) is used in combination with other anti-cancer drugs (e.g., antineoplastic chemotherapy, targeted agents). These other anticancer drugs can be administered concurrently or sequentially as part of a protocolspecific treatment regimen. The TMGs provide information for the management of immunemediated reactions, infusion-related reactions, and non-immune-mediated reactions that may be observed with monotherapy or combination ICI regimens, with specific instructions for ICI dose modifications (including discontinuation) and treatment interventions. Investigators are advised however to use local practice guidelines and consult local references for the management of toxicities observed with other anti-cancer treatment.

Dosing modification and toxicity management for immune-mediated, infusion-related, and nonimmune-mediated reactions associated with the use of a checkpoint inhibitor or checkpoint inhibitors in clinical study protocol (CSP) – whether that is durvalumab alone, tremelimumab alone, or durvalumab + tremelimumab in combination, or durvalumab +/- tremelimumab in combination with other anti-cancer drugs (i.e., antineoplastic chemotherapy, targeted agents) administered concurrently or sequentially – should therefore be performed in accordance with this Annex to CSP, which for the purposes of submission and approval of substantial updates is maintained as a standalone document. TMG updates are iterated by date, and should be used in accordance with the Common Terminology Criteria for Adverse Events (CTCAE) version specified in the CSP.

Although the TMG versioning is independent of the protocol, the TMG Annex to Protocol should be read in conjunction with the Clinical Study Protocol, where if applicable additional references for the management of toxicities observed with other anti-cancer treatment are included in the specific section of the Clinical Study Protocol.

